## **D.1. Measures to Minimize Potential Risks**

### D.1A Management of Risk due to due to Clinical and Cognitive Assessment Administration

At least one of the MD investigators will be available to address any mental health concerns and assist in appropriate referrals as needed. As noted above participants may refuse to answer any questions and take breaks as needed.

### D.1B Management of Risks due to tDCS.

Direct Current (DC) polarization has been applied unilaterally to the primary motor and dorsal prefrontal areas in many studies over the past decade (Wassermann, 2008) with no reports of adverse effects attributable to effects on the central nervous system. The proposed stimulation intensity in this study is similar to the stimulation intensity used in previous protocols as also performed at the NIH (and for which the risk determination from the FDA was requested). No adverse side-effects have been reported in these previous studies with the proposed stimulation settings. The proposed intensity level is therefore at the level at which we will expect to find effects of tDCS on our behavioral output measure, but without causing adverse side-effects. In a study measuring thermal effects of tDCS using a MRI-derived finite element human head model conventional rectangular-pad (7x5 cm^2) electrodes were found not to increase tissue temperature using a bio-heat model (Datta et al., 2009). In safety studies conducted at City College of New York (CCNY) and during usage at the National Institutes of Health (NIH), sets of these electrodes did not cause skin problems more serious than tingling and transient redness when applied to the skin of the arm with current densities up to 2.56 mA/cm^2 and durations of up to 22 minutes ([name], personal communication). It was also found that cathodal current produced the most skin irritation. However cathodal stimulation will be of crucial importance to our study design as we hypothesize that our target brain areas may be overactive, and hence require suppression. During cathodal stimulation we will take extra precautions that consist of instructing the participants to advise the research staff of any discomfort during testing, inspection of stimulation sites as needed and immediate discontinuing stimulation if discomfort occurs.

The tDCS device that will deliver the direct current is adjustable in both intensity as well as duration of stimulation. In addition, the device will be 9V battery-driven to function as a constant current stimulator with a maximum output in the milliamps range with absence of the risk of sudden large intensities of electrical current that could occur with an electrical driven device.

Prolonged passage of direct current across metallic electrode (where electrons from the stimulator are converted to ions carried through the body) can produce undesired electrochemical products such as pH changes. The sponge pocket will act to physically separate, and thus buffer, the skin from electrochemical changes. The normal saline used on the sponges assists in preventing burns. In addition, electrodes/sponges will not be placed over cuts, or skin lesions such as vascular moles and angiomas that might have greater conductance than the surrounding skin. One set of

Date most recently revised (m/d/y): 03/03/2015

Protocol Version (if applicable): 5.0

sponges will be used throughout the study for each participant. Electrodes will be held in place by using special head bands made of flexible rubber.

All participants will be carefully screened prior to tDCS for contraindications to tDCS (see exclusion criteria). At least one PI will be available on an immediate basis for all study treatment sessions.

tDCS will be administered by the tDCS Operator - a trained and qualified individual supervised by the principal investigators to deliver, or assist in delivery of, tDCS. Training includes the knowledge of safety considerations and precautions associated with tDCS.

Participants will be closely monitored throughout the study to assess for any adverse effects on cognition or mood. Participants will also be specifically instructed to tell the research staff if they notice an unwanted change in mood during the course of treatment.

The tDCS operator will:

- a) Assess the participants' scalp skin where the electrodes will be placed to assure it is intact, free of lesions, cuts or exclusionary skin disorders.
- b) Prepare and position the electrodes and tDCS device on the participant for accurate brain stimulation according to the protocol prior to initiation of stimulation.
- c) Operate the hardware associated with the tDCS device to assure the level of current and amount of time is accurate per protocol.
- d) Administer the tDCS, at the parameters established by the tDCS Attending Physician as per identified in this protocol.
- e) Assess the participants mental status and general clinical condition before and after tDCS to assure the safety of the participant to have tDCS and the safety of the participant to return home.
- f) Monitor the participant during the tDCS session to assess for potential occurrence of adverse events.
- g) Make routine adjustments to the placement of the device as required and consistent with product labeling (e.g., to ensure contact between participant's head and electrode) during the tDCS session. The tDCS Operator may not independently make any revision to pre-determined stimulation dose or electrode position parameters prescribed by the study protocol.
- h) Determine if tDCS should be interrupted or terminated (e.g., participants express increasing discomfort to their skin under the electrodes; participants show signs of discomfort or other stress; participant wants to discontinue study procedures).
- i) Take action in accordance with established Butler Hospital regulations in case of adverse events, for example: he/she will seek immediate medical attention for the participant if necessary; if there is any doubt about the mental or physical status of a participant after testing he/she will consult with the available study physician. He/she will document and report all adverse events (e.g. skin lesion or significant skin discomfort) to the principal investigators. A study physician will evaluate the participant and make a recommendation for immediate or follow-up care if required. Telephone or in-person follow-up will be arranged as needed. Any participant judged on clinical grounds to have suffered adverse effects will thus be evaluated and treated as necessary and withdrawn from the study.

Date most recently revised (m/d/y): 03/03/2015

Protocol Version (if applicable): 5.0

j) When not in use, assure the tDCS machine, electrodes, sponges, conductive gel, alcohol prep pads and normal saline are maintained in the secure location as assigned to [name] in a lockable room.

The experimenter will closely observe participants for signs of skin burns, discomfort, or other stress. Participants will have the option of discontinuing the study at any time and will be explicitly instructed to inform the experimenters immediately if they experience any discomfort. The experimenter will inform the supervising physician about any participant who has significant skin discomfort or a skin lesion after current delivery. If there is any doubt about the mental or physical status of an individual after testing, the principal investigators (or other supervising physician) will evaluate the participants and make a recommendation for follow-up care if that is required. Telephone or in-person follow-up will be arranged as needed. Any participant judged on clinical grounds to have been injured as a direct result of participation in this research will be offered emergency medical treatment by Butler Hospital paid for by research funds, except for costs that are covered by your insurance or governmental programs, and withdrawn from the study.

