The participant will then receive either the sham or active tDCS stimulation based on their random group assignment for twenty minutes (tDCS details are below). Following tDCS stimulation, only the DVPRS will be repeated. This measure will be used to determine whether immediate pain relief following stimulation occurs. Lastly, in order to monitor the effectiveness of the blind, participants will be asked to guess which treatment, active or sham, they received.

On subsequent treatment days, the DVPRS will be repeated before and after stimulation and the Sleep Measure will be repeated before stimulation. At the end of the first week of treatment, session five, in addition to the DVPRS and the Sleep Measure, the WHY-MPI, RMDQ, CPAQ-8, PHQ-9, GAD-7, and the PASS, will be repeated. During the second week, the DVPRS will again be administered before and after each treatment, and the Sleep measure will be repeated before stimulation.

On the final day of treatment, in addition to the DVPRS and the Sleep Measure, the WHY-MPI, RMDQ, CPAQ-8, PHQ-9, GAD-7, CEQ, CSQ-8, and the PASS, will be repeated.

Date most recently revised (m/d/y): 03/03/2015

Protocol Version (if applicable): 5.0

Follow-up assessments will occur by phone approximately six (6) weeks after the last tDCS treatment session and will consist of these same measures as session ten.

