**Risks due to tDCS:** There is some inherent risk with tDCS. Mainly there is a risk of skin irritation where the electrodes are attached to the scalp, which in the literature has been mostly limited to transitory redness. No toxic effects have been found, and the procedure carries few risks (Brunoni, et al., 2012). At the levels we are proposing, only a few publications report minor injuries, and the stimulation is widely considered to be “safe” (Bikson, et al., 2009). In rare cases, when skin around stimulation sites was non-intact, or when the stimulation was delivered for a long time without proper conductive solutions being applied to the electrodes, a few minor burns and skin lesions have been observed (Frank, et al., 2010). If electrodes/sponges are placed over preexisting skin lesions, such as vascular moles and angiomas there may be a greater conductance than the surrounding skin, increasing the risk of irritation or possible burns. Care is thus taken to exclude potential participants who exhibit broken or marked skin near the sites of the electrodes and to avoid abrading the skin prior to placing the electrodes (Loo et al. 2011). The electrodes in this study are soaked in normal saline. A study using the same amperage proposed in this protocol found no mood or cognitive changes due to tDCS (Iyer, et al., 2005). Transient, very rare post-tDCS effects have been found to include mild headaches, nausea, and insomnia (Poreisz, et al., 2007). In a prior study conducted by Drs. [name] and [name], eight of 40 participants reported sensations of itching, tingling, or burning under the tDCS electrodes; one participant reported mild dizziness. These sensations were consistent with those commonly reported for tDCS (Brunoni, et al., 2012). Less well-studied is the possibility of negative effects of tDCS on cognition and mood. A study using the same current amplitude as proposed in this protocol found no mood or cognitive changes due to tDCS, but this was with a single stimulation session (Iyer, et al., 2005). Several studies have used multiple sessions of tDCS of different brain regions successfully to reduce pain intensity from acute pain, neuropathic pain, and chronic pain from fibromyalgia (Antal, et al., 2008; Lefaucher, et al., 2008; Fregni et al. 2006) without significant adverse effects. Another potential concern is the risk of an undesired synergistic effect between a participant’s existing medication and tDCS. There are some reports in the literature of isolated instances of hypomanic or manic symptoms, typically noted with a longer treatment course than proposed in the current study or in patients with pre-existing bipolar diagnoses (Brunoni, et al., 2013; Galvez, et al., 2011) diagnosed bipolar disorder is an exclusion criterion for the present study. Nonetheless, comprehensive clinical studies quantifying the risk more precisely are clearly lacking. For the present study, participants will be closely monitored throughout the study to assess for any such effects. Participants will also be specifically instructed to tell the research staff if they notice an unwanted change in mood.

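### Monitoring of cognition and mood is promised throughout the study, but no dedicated measure of cognition or elevated mood is scheduled after screening, no contact is planned for about six weeks after session 10, and two sections differ on how long self-report runs

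*Combined protocol and SAP*

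**What the plan says.** Section C, Potential Risks (Risks due to tDCS), is candid about the uncertainty: "Less well-studied is the possibility of negative effects of tDCS on cognition and mood". It cites one study at the same current that "found no mood or cognitive changes due to tDCS, but this was with a single stimulation session"; this trial gives ten sessions (C2). It continues: "There are some reports in the literature of isolated instances of hypomanic or manic symptoms", qualified as typical of longer courses or of people with a prior bipolar diagnosis. It also names headache, nausea, insomnia, skin effects and, from a previous study, dizziness. It then promises that "participants will be closely monitored throughout the study to assess for any such effects", and tells participants to report an unwanted mood change, with no time limit.

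D.1B, Management of Risks due to tDCS, repeats the promise: "Participants will be closely monitored throughout the study to assess for any adverse effects on cognition or mood". Its self-report instruction has a limit: "Participants will also be specifically instructed to tell the research staff if they notice an unwanted change in mood during the course of treatment". Operator duty e) requires a look at mental status and clinical state around stimulation, duty f) requires adverse-event monitoring during the session, and duty i) covers documentation, reporting and physician evaluation.

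Table 1 places the MINI at screening only. PHQ-9 (depression) and GAD-7 (anxiety) are at sessions 1, 5 and 10 and at follow-up, and the sleep measure is at every session and at follow-up. The only planned contact after session 10 is a telephone call about six weeks later, whose assessments "will consist of these same measures as session ten" (C3).

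**The concern.** The promise covers the whole study, but the schedule does not supply the means. The two harms that the protocol singles out as poorly studied, change in cognition and elevated mood, have no dedicated measure in Table 1 after screening. For most of the study's calendar time nobody is due to ask. The self-report instruction adds little for hypomania, because it asks about an unwanted change and a participant may welcome an elevated mood.

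What is at stake is safety ascertainment. A participant whose mood becomes elevated, or whose thinking changes, after session 10 has no scheduled question aimed at finding it. During treatment, whatever is found depends on an unstructured check. C2 states blinding for participants and for staff who administer outcome scales, but does not say whether the operator is blinded. Counts collected that way are hard to compare between arms.

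**Working it through.** No sample-size or power figure is involved. The check has two parts: a count of study time, and a comparison of each harm with what is scheduled for it.

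**Study time.** Inputs: ten sessions on consecutive weekdays and a call approximately six weeks after the last (C2). The advertisement gives a two-week treatment period.

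- Ten consecutive weekdays starting on a Monday span 12 calendar days. Starting on any other weekday, they cross two weekends and span 14 days. This reproduces the stated two weeks.
- Six weeks = 6 × 7 = 42 days.
- Session 1 to the call: 12 + 42 = 54 days, or 14 + 42 = 56 days.
- Share with no planned contact: 42/56 = 75%; 42/54 = 78%.

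**Checks during treatment.** Reading duty e) as applying at each session: 2 checks × 10 sessions = 20 per participant, all on or before the day of session 10.

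**Coverage by harm.**

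| Harm | Sessions 1 to 10 | Session 10 to the call | At the call |
|---|---|---|---|
| Depressed or anxious mood | PHQ-9 and GAD-7 at sessions 1, 5, 10; operator check | No planned contact | PHQ-9, GAD-7 |
| Insomnia | Sleep measure | No planned contact | Sleep measure |
| Elevated mood | Operator check; self-report if unwanted | Self-report only, and only under the Potential Risks wording | No dedicated measure |
| Cognition | Operator check | No planned contact | No dedicated measure |
| Headache, nausea, dizziness | Operator's general check; no symptom question stated | No planned contact | No question stated |
| Skin effects | Operator inspection and observation | No planned contact | No question stated |

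**Whether another section fills the gap.** The risk sections refer to cognitive assessment and section 7 lists cognitive test results as data needed, but no cognitive test appears in Table 1 or in the visit descriptions. The Data Safety Monitoring Plan (D.3) deals with storage, coding, access and training, not with collecting adverse events. C4 plans no safety analysis. Further telephone or in-person follow-up is arranged only as needed, so it depends on a problem already being known.

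**The case against.** The strongest case on the other side is that the treatment period is well covered. Twenty mental-status checks per participant are required, adverse events are monitored in session, and events must be recorded, reported and seen by a physician. After sessions 1 to 9, the next visit's check can pick up what arose at home. This stands. A reader might infer that cognition and elevated mood go unobserved for the whole study, and the documents do not support that. What is missing during treatment is a named instrument or fixed question.

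A reader might also infer that the self-report instruction lapses when treatment ends. That is true of D.1B only; the Potential Risks section sets no end date. The supportable finding is a disagreement between two sections. Nor is mood unmeasured after treatment: depression, anxiety and sleep are all scheduled at six weeks.

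The protocol says manic symptoms were typically seen with longer courses or in bipolar disorder. Lifetime bipolar disorder is excluded and screened for by the MINI. This lowers the expected frequency of hypomania. It does not bear on cognition, headache or nausea, and the protocol itself says that precise risk data are lacking and promises monitoring regardless.

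Finally, no aim or planned analysis sets out to conclude that ten sessions are harmless, and a checklist could not support that claim either. With no events among 10 active participants, the one-sided 95% upper bound is 1 − 0.05^(1/10) = 26%. This also stands. The benefit of a checklist is that both arms are asked the same thing, not that it could demonstrate safety. The 75 to 78% likewise weights quiet follow-up days equally with days of stimulation; it describes contact, not risk.

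**Conclusion.** The concern holds within limits. The protocol states a property, monitoring of cognition and mood throughout the study, that its schedule does not deliver. Dedicated measures of cognition or elevated mood after screening: none. Adverse-event questions in Table 1: none. Time from session 1 to the call without planned contact: 42 of 54 to 56 days, 75 to 78%. In addition, Potential Risks and D.1B disagree on the duration of the self-report instruction.

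This rests on three assumptions. The ten sessions run without gaps, and the call falls at exactly 42 days although the protocol says approximately. Duty e) applies at every session. The scope of the questionnaires is taken from their labels in Table 1 and their descriptions in C3; the items are not printed in the protocol, so incidental coverage by a single item cannot be excluded, and the finding is confined to dedicated measures.

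The gap concerns safety ascertainment and does not affect the efficacy comparisons. Even in an exploratory study of 20 it should be corrected, because the promise is explicit and the remedy is small.

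**What to change.** - **Checklist.** Add one brief fixed symptom checklist to Table 1, identical in both arms, before each session (events since the last visit), after session 10, and at the six-week call (events since session 10). Limit it to harms the protocol already names: skin effects, headache, nausea, dizziness, hypomanic or elevated mood, and change in cognition. Insomnia is already reached by the sleep measure.
- **Who asks.** At visits the participant completes it, and it is kept from the blinded outcome raters. At the call, existing study staff other than the blinded rater ask it. C3 has all questionnaires done with help from blinded personnel, so this exception must be written in.
- **Self-report.** Reconcile Potential Risks and D.1B so that the instruction covers the same period as the monitoring promise, and word it neutrally, for example *any marked change in mood*.
- **Handling of answers.** Send positive answers to the study physician. Duty i) of D.1B links a clinical judgement of adverse effects to withdrawal, so the sponsor should reconcile that wording with solicited minor symptoms and make clear how they are handled. No rule is proposed here.

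Cost: 10 pre-session forms + 1 after session 10 + 1 at the call = 12 per participant. At about two minutes each that is 24 minutes, or 20 × 24 = 480 minutes (8 hours) for the whole trial. No new visits or calls are needed. The main downside is that solicited questions will record more minor events in both arms.

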### **C2. Study Design**

The study includes a screening visit, ten (10) study treatment session visits on consecutive weekdays and a follow-up phone call, approximately six (6) weeks after the last study visit. The ten study visits will occur at Butler Hospital and will take between two (2) to two and half hours (2 ½) hours. The total duration of this study for the participant is expected to be up to approximately twenty- four (24) hours; this includes the consent process, screening and eligibility assessments and ten research visits which will include the study treatment, tDCS, completion of study related questionnaires, and the follow-up phone call.

Half of the participants will receive only sham stimulation for all treatment days (days where tDCS is applied) and half will receive only active stimulation; this will be randomly assigned. Comprehensive measures of distress resulting from CLBP will be administered to assess both the short and longer term effects of tDCS treatment. Participants and research staff administering outcome scales will be blinded to active vs. sham tDCS.

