#### D. Material Inducements

Date most recently revised (m/d/y): 03/03/2015

Protocol Version (if applicable): 5.0

Compensation for time and effort will be offered for the measures administered in this study. Participants will receive \$60 as compensation for participation if they complete all 10 sessions of tDCS treatment. If the participants withdraw from the study before finishing, they will receive \$6 per session for each session in which they participated regardless if they were able to complete the full session.

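### Participants judged to have adverse effects leave the study, not just stimulation; on the natural reading their remaining outcome scales stop, and no section says they continue

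*Combined protocol and SAP*

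**What the plan says.** Section D.1B has two clauses that take a participant out of the study. Item i of the operator's duties reads: "Any participant judged on clinical grounds to have suffered adverse effects will thus be evaluated and treated as necessary and withdrawn from the study". The closing paragraph of D.1B applies the same consequence to a differently worded trigger: "Any participant judged on clinical grounds to have been injured as a direct result of participation in this research".

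Stopping the current is dealt with in other words. The opening paragraph of D.1B has stimulation discontinued if discomfort occurs. Item h lets the operator "Determine if tDCS should be interrupted or terminated" and says nothing about study status.

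The contact that D.1B describes after an event is: "Telephone or in-person follow-up will be arranged as needed". It follows a sentence on recommendations for care and names no outcome scale.

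Under C3 and Table 1, WHYMPI, RMDQ and PASS-20 are taken at session 1, session 5, session 10 and six weeks. The DVPRS is also taken before and after every session. C3 times the last contact as follows: "Follow-up assessments will occur by phone approximately six (6) weeks after the last tDCS treatment session". Section C4 lists linear and mixed models but states no analysis set and no rule for missing scores.

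**The concern.** Withdrawal under these clauses happens after randomisation and may be caused by the treatment. If it ends the scales, the data lost are not a random sample.

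Hypotheses 1.1, 1.2, 2.1 and 2.2 rest on WHYMPI, RMDQ and PASS-20, which have only three post-baseline time points. Someone withdrawn in sessions 1 to 4 would have none of them, and no model named in C4 can supply an observed change for that person. Hypothesis 1.3 is less exposed because of the session-by-session DVPRS.

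The clauses cover both arms. Greater loss in the active arm is plausible, because C3 sets up to 2 mA for 20 minutes against 40 seconds at 1 mA in sham, but nothing in the documents demonstrates it. If those withdrawn would have scored worse than the rest, the comparison favours the arm that loses more. If they would have scored better, the reverse holds.

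**Working it through.** **Reading the text.** Three features point to the end of participation rather than of stimulation alone: the separate wording for stopping current, the object of the withdrawal (the study), and the lack of any section that keeps the scales going.

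**Inputs.** From the documents: 10 participants per arm (C1), 10 sessions, and scales at sessions 5 and 10 and at six weeks (C3). C4 gives no power analysis, so there is no planned figure to reproduce. Assumed: withdrawal rate p in the active arm of 2.5%, 5% or 10%; no sham losses; correlation ρ of 0.3 or 0.5 between propensity to be withdrawn and outcome; no true effect. The only event counts given are from a prior study: "eight of 40 participants reported sensations of itching, tingling, or burning under the tDCS electrodes; one participant reported mild dizziness". These are events, not withdrawals.

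**Chance of loss.** At least one of 10 active participants: 1 − (1 − p)^10. With withdrawals spread evenly over the 10 sessions, at least one with no post-baseline score: 1 − (1 − 0.4p)^10.

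**Scores lost per withdrawn participant.** Sessions 1–4 lose three, 5–9 lose two, and 10 loses one: (4×3 + 5×2 + 1×1)/10 = 2.3 of 3. If the scales due at the session of withdrawal are lost as well: (5×3 + 5×2)/10 = 2.5.

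**Observed-case bias.** Suppose the k active participants with the highest propensity of 10 are lost. The mean of those left shifts by ρ × S_k/(10 − k), where S_k is the expected sum of the k largest of 10 standard normal values: S_1 = 1.539, S_2 = 2.540.

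- k = 1: 0.3 × 1.539/9 = 0.051 SD; 0.5 × 1.539/9 = 0.085 SD.
- k = 2: 0.3 × 2.540/8 = 0.095 SD; 0.5 × 2.540/8 = 0.159 SD.

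Averaging over k ~ Binomial(10, p):

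| p | at least one lost | at least one with no post-baseline score | bias, ρ = 0.3 | bias, ρ = 0.5 |
|---|---|---|---|---|
| 2.5% | 22% | 10% | 0.013 SD | 0.021 SD |
| 5% | 40% | 18% | 0.025 SD | 0.041 SD |
| 10% | 65% | 34% | 0.049 SD | 0.081 SD |

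The standard error of a 10 v 10 difference is √(2/10) = 0.447 SD, so the bias is about 3% to 18% of it.

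**Variations.**
- Sham loses at half the active rate: 0.006 to 0.039 SD.
- Equal rates, or ρ = 0: zero.
- Loss follows a fixed threshold, with bias ρφ(z)/(1 − p) and z the upper-p normal quantile: 0.018 to 0.098 SD.
- Ceiling of p = 20%, which would need every one of the 8/40 sensations to lead to withdrawal: 89% chance of a loss, bias 0.09 to 0.16 SD. The text does not suggest this.

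**Mixed model.** A simulation (40,000 runs, ρ = 0.5, assumed correlation 0.6 between session 5 and session 10 scores, loss after session 5) gave bias within 0.003 SD of zero when loss depended on the session 5 score. When it depended on the session 10 score, bias was 0.059 (k = 1) and 0.106 SD (k = 2), against 0.089 and 0.163 for observed cases. This helps only participants who reached session 5.

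**With continued collection.** If a share q of those stopped complete their scales, the threshold-model bias becomes ρφ(z)(1 − q)/(1 − p(1 − q)). Over p from 2.5% to 10% and both values of ρ, it falls from 0.018–0.098 to 0.009–0.046 SD at q = 0.5, and to 0.004–0.018 SD at q = 0.8.

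**The case against.** The strongest reply is that the loss is inferred from a safety clause in a list of operator duties, not from a data-collection rule. A reader might infer that the protocol forbids later scales. It does not. C3 dates the call from the last stimulation session and does not limit it to people who complete ten, so a call after early stopping would fit the text. The consent form (not in the text reviewed) and the hospital regulations to which item i defers may also say more. This stands, and it limits the claim to a natural reading. Sessions 5 and 10 would still be unaddressed.

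Three further inferences are not supported:

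- *That the payment section settles the meaning.* Section D, Material Inducements, has "If the participants withdraw from the study before finishing", but it sets this against completing ten stimulation sessions. It concerns departure by the participant's own choice, and payment only. It is weak evidence either way.
- *That the six-week call has two conflicting dates.* C2 has "a follow-up phone call, approximately six (6) weeks after the last study visit", while C3 counts from the last stimulation session. On the normal schedule these are the same day. The date becomes unclear only for someone who stops early.
- *That the trial's result is materially biased.* D.1B reports no adverse side-effects at the proposed settings in previous studies. The 8/40 count covers ordinary sensations and is not split by arm. No rate, imbalance or correlation is documented.

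It is also fair to say that Hypotheses 1.1 and 1.2 concern ten days of stimulation, so scores after early stopping answer a somewhat different question. That argues for showing both summaries. Scores never collected leave only one.

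**Conclusion.** The point holds as a cheap improvement that should be made, with medium confidence. D.1B states a rule that, followed on its natural reading, ends outcome collection after an event that may depend on treatment. A participant withdrawn in sessions 1 to 4 would contribute no post-baseline WHYMPI, RMDQ or PASS-20 score.

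The expected size is small even under the one-sided assumption of no sham losses, and every figure rests on assumed rates and correlations. One or two actual losses would give 0.05 to 0.16 SD on observed cases. In an exploratory 10 v 10 study, the low cost of the change is the main argument for it, not a demonstrated bias.

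**What to change.** Leave when and why stimulation is stopped exactly as it is.

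- In item i and the closing paragraph of D.1B, reword the consequence so that it does not end data collection. Adding a sentence beside the present wording would only create a contradiction.
- Then add: *A participant removed under this clause is still asked to complete the remaining scheduled scales at the planned session 5, session 10 and six-week dates, in person or by phone, unless he or she withdraws consent.*
- In C2 and C3, date the six-week call for early stoppers from their planned session 10 date.
- In C4, include these scores in the assigned arm in the mixed model already listed. An on-treatment summary can be shown alongside.
- The investigators should reconcile the two differently worded triggers (adverse effects, and injury directly due to participation). No view is taken here on which applies.

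**Cost.** A few sentences. At the assumed rates, 10 × 0.025 = 0.25 to 10 × 0.10 = 1 active participant is expected to be affected, each needing at most three assessments with instruments already in use and already planned by phone at six weeks. Some will decline, and scores after early stopping may slightly dilute the effect of a full ten-session course.
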